In determining the sample size of 218 needed to recruit for the study, we examined the number of patients needed to have adequate power to detect differences between the intervention and usual care groups using the mean DDS17 score as the primary outcome. The sample size was initially based on testing for a medium effect size ($d = .50$) between the intervention and usual care groups at a single time point, using a two-group t test with a 0.05 2-sided significance level and power of 80%. Because we will assess participants at three time points (baseline, posttreatment, and 6 months), this estimate was then adjusted to account for the correlation among the repeated measurements, using the adjustment factor $[1 + (T-1)\bar{\rho}]/T$, where T is the number of follow-up measurements and $\bar{\rho}$ is the correlation coefficient of the repeated measurement. In our study, $T = 2$ follow-up measurements after baseline, and $\bar{\rho}$ is estimated using the relatively high value of 0.5. The sample size determined for the primary outcome was inflated to account for attrition of 30% at 6 months. In a VHA-funded investigator-initiated grant (Behavioral Activation Therapy for Rural Veterans with Diabetes and Depression; PI: [name]), on which members of the research team are co-investigators, attrition at 6 months was 16.9%. Because this study will include Veterans from VHA and non-VHA settings, we estimated attrition to be somewhat higher than what we

found in the study of patients from VHA settings only. Thus, a sample size of 134 patients would need to be recruited (67 in the intervention group and 67 in usual care) for 80% power to find important differences in the DDS17 measures.

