However, to have power to address the secondary outcomes and because only a portion of the recruited Veterans will have anxiety and depression, we increased the sample size of 134 by 62.7% as described below, resulting in 218 Veterans to be recruited. Although all eligible participants will have diabetes-related distress, we expect depression and anxiety to be prevalent in 25% or more of participating Veterans. Fisher et al. found that 22.5% of those with high diabetes-related distress were clinically depressed. For these secondary outcomes, we initially calculated the sample size based on testing for a large effect size ($d = .80$) between the intervention and usual care groups at a single time point, using a two-group t test with a 0.05 two-sided significance level and power of 80%. Adjusting this to account for correlation among repeated measures results in 18.4 participants per group. Finally, adjustment for 30% attrition at 6 months results in a total needed of 27 per group. Therefore, we need to recruit 218 Veterans, of whom we expect 25% (54) to have anxiety and depression. Thus, we will have 80% power to detect a large effect size of .80 for the secondary outcomes of PHQ-8 and GAD-7. If we based the sample size for the secondary outcomes on detecting a medium effect size of .50, the required sample size of 134 patients would mean increasing the total to 536 patients, a number not feasible for this grant (25% of 536 patients = 134 with anxiety and depression).

In our prior work involving similar recruitment methods, we expect that approximately 7% of those referred to the study from VHA patient databases or community partners will be enrolled in the study (i.e. contact made, interested and eligible for the study). Therefore, we estimate that we will need to attempt to contact approximately 3,114 potential subjects in order to enroll 218 patients in the study.

G2. Data Analysis

Provide a description of your plan for data analysis. State the types of comparisons you plan (e.g. comparison of means, comparison of proportions, regressions, analysis of variance). Which is the PRIMARY comparison/analysis? How will the analyses proposed relate to the primary purposes of your study?

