Outcomes: Primary outcome. We will compare participants in the 2 study arms on baseline characteristics, including sociodemographic characteristics and clinical variables. Based on the Consolidated Standards of Reporting Trials recommendations, we will not provide tests of significance or adjust subsequent analyses for variables found to differ because adjustment may bias the estimated treatment effect. However, because socioeconomic status (SES) and race/ethnicity might impact the mechanism of navigation/coaching, we will include the SES (income and education) and race/ethnicity variables as a priori covariates in our regression analyses. We will examine distributions of the primary outcome (DDS17) and consider transformations, if necessary. We will test for differences between the active intervention and usual care groups using continuous dependent measures (either untransformed or transformed if needed). The random coefficient model will allow us to fit a line for each participant using his/her available data, including participants with missing values, and will maximize the power to detect differences because participants are not removed from the analysis if any time period is missing. Analyses will contain a variable indicating the treatment group, a variable representing the referral source (MEDVAMC and non-MEDVAMC [community social service agencies, or VSOs]), SES and race/ethnicity variables, a variable indicating time (baseline, 3 months, or 6 months), and a term for the interaction of time and treatment. The time-by-treatment interaction is of most interest in this repeated measures analysis because a significant value will indicate a difference between groups over 6 months.

The treatment effect will measure differences between the groups at baseline, and the time effect will measure outcome change over time. By dichotomizing the outcome, we will determine whether the groups differed proportionally in clinically significant improvement on the DDS17. A value of 2.9 or less for the DDS17 will be considered as indicating little or no distress to moderate distress; a value of 3.0 or more will represent high distress. We will test this difference using a logistic regression model in which the dichotomous outcome is the dependent variable. Independent variables will be those for the linear regression models.

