Outcomes: Secondary outcomes. Analyses of the secondary clinical outcomes will be similar to those used for the continuous primary outcomes. We will test assumptions of normality and make transformations as needed. We will then run linear regression models separately for each secondary outcome. The models will include terms for the intervention, time period, time-by-period interaction, the a priori SES and race/ethnicity variables, and the referral source. Significant values for the time-by-treatment interaction will indicate that there were significant differences over time in the secondary outcome. In addition, by dichotomizing the outcomes, we will determine whether the groups differed in having or not having clinically significant changes in PHQ-8 and GAD-7 scores. A 5.0-point decrease in the value of PHQ-8 will be considered a minimally clinically important change⁹⁴ and coded as such; decreases of less than 5.0 points from baseline will be coded as not having achieved clinically significant change. For GAD-7, a score of less than 10 will be considered as having clinical improvement, with scores of 10 or higher representing clinically elevated anxiety symptoms. We will test whether the two groups (clinically significant change vs. no clinical change) differed using a logistic regression model in which the dichotomous outcomes are the dependent variable. The independent variables will be those described above for the linear regression models.

For the secondary outcomes of use of printed/web-based resources, health promotion programs, and clinical care, we will run logistic regression analyses of dichotomized variables (i.e., whether or not the patient used printed/web resources, whether or not he/she used health promotion programs, and whether or not he/she used clinical care during the 6-month follow-up). The models will include terms for the intervention, the a priori SES and race/ethnicity variables, and the referral source. Significant values for the treatment term will indicate that there were significant differences between the iNSPiRED and usual care groups.

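### The 80% power at d = 0.80 for PHQ-8 and GAD-7, which lifts enrolment from 134 to 218, is calculated for about 54 symptomatic participants, but the planned analyses of these outcomes are not restricted to them.

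*Combined protocol and SAP*

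**What the plan says.** G1 first arrives at 134 participants for the primary outcome, DDS17. It then increases that number by 62.7% to serve the secondary outcomes, "because only a portion of the recruited Veterans will have anxiety and depression". For PHQ-8 and GAD-7 it assumes d = 0.80, two-sided alpha 0.05 and 80% power. A repeated-measures adjustment brings the requirement to 18.4 per group, and 30% attrition brings it to 27 per group. It continues: "Therefore, we need to recruit 218 Veterans, of whom we expect 25% (54) to have anxiety and depression". The power statement follows: "Thus, we will have 80% power to detect a large effect size of .80 for the secondary outcomes of PHQ-8 and GAD-7". G1 also gives the alternative it rejected: at d = 0.50 it would need 134 symptomatic participants, hence 536 enrolled.

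G2, under Outcomes: Secondary outcomes, says: "Analyses of the secondary clinical outcomes will be similar to those used for the continuous primary outcomes". On the model it says: "The models will include terms for the intervention, time period, time-by-period interaction", followed by SES, race/ethnicity and referral source. The next sentence but one refers to the time-by-treatment interaction, which is evidently what is meant. No baseline symptom threshold, symptomatic subset or symptom-by-treatment term appears. The PHQ-8 5-point decrease and the GAD-7 threshold of 10 are used to code dichotomous outcomes.

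**The concern.** Power belongs to a particular test in a particular set of participants. G1 calculates it for a symptomatic quarter of the sample; G2 tests everyone. Entry (F1, Inclusion Criteria) requires diabetes distress but not depression or anxiety, so the two sets differ by a factor of about four.

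The sentence matters because it is the stated reason for 84 of the 218 participants (218 - 134 = 84). A null PHQ-8 or GAD-7 result would be read against an 80% figure that belongs to a different analysis set. If the symptomatic group were chosen as the target only after results by arm were known, its cut-off could be influenced by the data, because G1 does not define it.

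**Working it through.** **1. G1's own figure.** Inputs from G1: d = 0.80, two-sided alpha 0.05, power 80%, T = 2, correlation (rho) 0.5, 30% attrition, 25% symptomatic.

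- Per group at one time point: 2 × ((1.960 + 0.842)/0.80)² = 24.53.
- Repeated-measures factor [1 + (T-1)rho]/T, "where T is the number of follow-up measurements": (1 + 0.5)/2 = 0.75. 24.53 × 0.75 = 18.40, as stated.
- Attrition: 18.40/0.70 = 26.28, rounded up to 27 per group, 54 in total, as stated.
- Enrolment: 54/0.25 = 216; 134 × 1.627 = 218.0; 25% of 218 = 54.5. This agrees with 218 to within rounding.
- The rejected option, 134/0.25 = 536, uses the same logic: only symptomatic participants are counted.

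**2. Power for the analysis in G2.** Inputs: 109 per arm (218, 1:1) and 30% loss, so 109 × 0.70 = 76.3 completers per arm. Assumptions: common SD, and equal correlation rho between all three time points.

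G2 does not fix the time-by-treatment contrast for these outcomes. The primary-outcome text says "The random coefficient model will allow us to fit a line for each participant using his/her available data", which suggests a slope, while the secondary-outcome text speaks of time period. Both are shown. The variance factors f are:

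- average follow-up change from baseline: (1 + rho)/2 + 1 - 2rho = 1.5(1 - rho), or 0.75 at rho = 0.5;
- linear slope over three equally spaced points, expressed as the month-6 difference in change: 2(1 - rho), or 1.0 at rho = 0.5.

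The detectable effect is approximately 2.802 × √(2f/76.3). At rho = 0.5 this gives 0.393 and 0.454; the t-test version gives 0.395 and 0.457.

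| Whole sample, completers, 80% power | rho 0.3 | rho 0.5 | rho 0.7 |
|---|---|---|---|
| Average change | 0.47 SD | 0.40 SD | 0.31 SD |
| Slope, month-6 difference | 0.54 SD | 0.46 SD | 0.35 SD |

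The primary-outcome text in G2 keeps participants with partial data. Under generalised least squares on available data at rho = 0.5, with the 30% loss falling all at month 6, half at each visit, or all by month 3, the detectable effect is 0.34 to 0.37 SD (average change, effect constant from month 3) or 0.43 to 0.44 SD (slope).

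A random coefficient model also allows slopes to vary between participants, which breaks the equal-correlation assumption. Adding 0.10 to 0.50 SD² of slope variance over 6 months (an assumption) raises the completer slope figure to 0.457 × √1.1 = 0.48 up to 0.457 × √1.5 = 0.56.

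**3. Two scenarios for the whole-sample test, rho = 0.5, completers.**

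- Everyone gains 0.80: power exceeds 99% for either contrast.
- Only the symptomatic 25% gain 0.80, the rest gain zero, SDs equal (all assumptions): the average effect is 0.25 × 0.80 = 0.20, and power is 29% (average change) or 23% (slope). If the subset SD is 0.6 to 0.8 of the whole-sample SD, the average effect is 0.12 to 0.16, and power is about 14% to 21% or 11% to 17%.

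**4. The symptomatic subset itself.** Using G1's factor of 0.75, 30% loss and a t test at d = 0.80, power is about 79% with 54 participants (25%). It is about 75% with 49 (218 × 0.225), the share G1 cites from another study in which "22.5% of those with high diabetes-related distress were clinically depressed". It is about 86% with 65 (218 × 0.30), which G1's own expectation of 25% or more allows.

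**The case against.** The strongest reply is that the mismatch errs in a safe direction. The objective in Section D is that intervention Veterans improve more on PHQ-8 and GAD-7, without restriction to those with symptoms. For an effect shared by all, 218 participants give far more than 80% power at 0.80. That stands. A reader might infer that the trial is underpowered for these outcomes, but the documents do not support this: the low figures need a benefit confined to the symptomatic quarter and exactly zero elsewhere, which no section predicts. The documents also give no SDs, so those figures are illustrative.

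A second reply is that a subset was implied, since scoring below 10 on GAD-7 as improvement makes most sense for people who start above 10. This is possible. But those thresholds are written as outcome codings, and later in G2 the authors name a subset explicitly when they want one, for new use of VHA or community care. If a subset was intended, it has no cut-off, and G1 leaves open whether depression, anxiety or both are required.

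A third reply is that these are secondary outcomes and the remedy is wording. That is true, and it limits the severity. A reader might also carry the question about the contrast over to DDS17 and infer that the primary outcome is underpowered. That is a separate matter and not part of this point. At 218, rho = 0.5 and d = 0.50, completer power for DDS17 is about 87% for a slope and 94% for average change.

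**Conclusion.** The point holds as a mismatch between the sample-size statement and the analysis. The 80% at d = 0.80 belongs to about 54 symptomatic participants and does not describe the PHQ-8 and GAD-7 tests in G2. A reader might infer an arithmetic error in G1, but every step of its chain reproduces.

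For the planned whole-sample test, the effect detectable with 80% power is roughly half of 0.80 or a little more: 0.40 SD (average change) or 0.46 SD (slope) among completers, and somewhat smaller if partial data are kept. These figures assume 30% loss, rho = 0.5 and equal correlation. The 23% to 29% power applies only under the confined-benefit assumption with equal SDs, and is lower if the subset SD is smaller. The trial is not invalidated, but the statement that justifies the larger enrolment should be corrected.

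**What to change.** Before any outcome is compared by arm, do one of the following.

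(i) **Keep the whole-sample analysis** and replace the 80%-at-0.80 sentence in G1 with the effect detectable in all participants. Name the time-by-treatment contrast in G2 and say how dropouts are handled. With 218 enrolled, 30% loss, rho = 0.5 and equal correlation, the figures to state are:

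- average change from baseline: about 0.40 SD among completers (0.31 to 0.47 for rho 0.7 to 0.3), or about 0.34 to 0.37 SD if partial data are kept;
- month-6 slope difference: about 0.46 SD among completers (0.35 to 0.54), or about 0.43 to 0.44 SD if partial data are kept, with a note that random-slope variance would raise these.

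(ii) **If symptomatic Veterans are the target**, pre-specify in G2 one PHQ-8 analysis and one GAD-7 analysis, each in participants elevated at baseline on that same measure, with stated cut-offs. Give power over a range of subset sizes. On G1's factor this is about 75%, 79% and 86% at 22.5%, 25% and 30% of 218; recompute it if the chosen contrast, or the correlation within the subset, differs.

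The cost is wording in G1 and G2 and restated figures, with no extra participants. The published power figures will change. Option (ii) also adds two small analyses whose sizes are not known in advance and, because randomisation is stratified by referral source only, may not split evenly between arms.

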Patients will be eligible to participate in the study if they meet the following criteria:

(1) Veteran (2) Diagnosis of type 2 diabetes mellitus, per self-report (3) Moderate diabetes-related distress (Diabetes Distress Scale [DDS2] mean score of 3 or greater)

Exclusion Criteria:

(1) Lack of reliable access to a telephone (2) Cognitive, sensory, or other impairment that prevents use of a telephone (3) Current participation in another diabetes-related counseling or self-management program

F2. Procedure

Upon providing informed consent, participants will be randomized in blocks of 6 or 8, based on referral source (MEDVAMC and non-MEDVAMC). At the initial screen, the study staff will confirm eligibility. Veterans will be screened for distress using the 2-item screening version of the Diabetes Distress Scale. Veterans with a mean score of 3 or more will be eligible to continue. Veterans who are eligible and wish to participate further will be scheduled for a telephone baseline assessment. They will be mailed a cover letter, informed consent document without signature lines, and copies of baseline assessment instruments. A member of the study team will call and review the consent documents before final enrollment and completion of the baseline assessment.

Usual care. Veterans randomized to the usual care condition will be encouraged to follow-up with their primary care provider and/or specialty providers for management of their health conditions. They will receive a packet of printed information that includes a list of self-management support resources in the VHA and the local community, but no specific recommendations or referrals. The list will be updated periodically with similar resources as needed.

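### In the linear repeated-measures models, referral source, SES and race/ethnicity enter only as main effects, so the randomisation stratum is not carried into the tested time-by-treatment contrast

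*Combined protocol and SAP*

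**What the plan says.** Section F2 (Procedure) states that "participants will be randomized in blocks of 6 or 8, based on referral source", with two strata, MEDVAMC and non-MEDVAMC.

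Section G2 (Outcomes: Primary outcome) describes a random coefficient model for the DDS17 at baseline, 3 months and 6 months. The listed terms are treatment, referral source, SES, race/ethnicity, time, and one interaction, time with treatment. On the covariates it says "we will include the SES (income and education) and race/ethnicity variables as a priori covariates in our regression analyses", because they may affect how navigation and coaching work. The treatment main effect is said to capture the baseline difference, so baseline is part of the outcome vector. The tested term is stated directly: "The time-by-treatment interaction is of most interest in this repeated measures analysis because a significant value will indicate a difference between groups over 6 months".

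Section G2 (Outcomes: Secondary outcomes) uses the same set of terms for the continuous secondary scores. The interaction is labelled differently there at one point but is interpreted as time-by-treatment. Neither paragraph lists a covariate-by-time term.

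**The concern.** The tested quantity is a difference between arms in change over time. A covariate that is fixed for each participant and enters as a main effect raises or lowers all of that participant's visits by the same amount, so it describes level and not change. A reader of the trial report would take the primary test to be adjusted for the stratification factor and the pre-specified covariates. In the linear models that is barely so.

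Precision is at stake. Stratified randomisation balances referral source between arms and so removes its contribution to chance differences in change. If the model has no term for how change differs by referral source, that variation stays in the residual and the reported SE is larger than it need be. Referral source could plausibly predict change: section D describes Veterans outside the healthcare system as less engaged in care, and section G1 expects more attrition because non-VHA settings are included.

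**Working it through.** **1. The plan's own sample size (section G1).** Inputs: d = 0.50, two-sided 0.05, 80% power; repeated-measures factor [1+(T−1)ρ]/T with T = 2, where ρ "is estimated using the relatively high value of 0.5"; and a size that "was inflated to account for attrition of 30% at 6 months".

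- n per arm = 2(1.960+0.842)²/0.50² = 62.79
- × (1+0.5)/2 = 0.75 gives 47.09
- ÷ 0.70 gives 67.28 per arm, 134.6 in total

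The stated 134 (67 per arm) reproduces. Nothing below changes 134 or 218.

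**2. Complete data: algebra.** Let x be a baseline covariate with main-effect coefficient c. Fitting c amounts to subtracting c·x from every visit of a participant. Each arm's mean then moves by c times its mean of x, by the same amount at all three visits. Only the arm's intercept moves. The difference in change, and hence time-by-treatment, does not.

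**3. Complete data: numerical check.** Simulated trials of 218 (109 per arm). Assumed values, none of them in the documents: intercept variance 0.6, slope variance 0.3, covariance −0.15, residual SD 0.5, 6-month effect −0.40, moderate covariate effects on level and slope.

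| Model | Largest change in the interaction estimate, main effects vs no covariates |
|---|---|
| GLS, linear time | about 4×10⁻¹⁶ |
| GLS, categorical time | about 2×10⁻¹⁵ |
| ML mixed model | about 3×10⁻¹⁴ |

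The GLS SE is 0.1212 with and without the main effects.

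**4. With about 30% missing at month 6.** Participants seen at month 6 now differ from those seen at baseline, so the shift no longer cancels exactly.

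- Missing completely at random: the estimate moves with SD 0.017–0.019, at most 0.059. The GLS SE stays at 0.137. In ML mixed models it goes from 0.1394 to 0.1370 (ratio 0.983); a separate set of 60 simulated trials gave 0.995.
- Missingness related to arm and covariates (29%): the mean estimate moves from about −0.375 to −0.399 (truth −0.40), with a largest single shift of 0.088.

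**5. What by-time terms could gain.** With complete data and linear time, the slope estimate is month 6 minus baseline. Its variance per participant is 0.3 + 2×0.25 = 0.80, plus whatever covariates contribute to change. Under the assumed effects, referral source (0.3 per 6 months, half in each stratum) adds 0.3²×0.25 = 0.0225 and income (0.15 per SD) adds 0.15² = 0.0225, for a total of 0.845.

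- SE as planned: √(0.845×2/109) = 0.1245
- With referral source-by-time: √(0.8225×2/109) = 0.1228, ratio 0.987 (1.3% smaller)
- With income-by-time as well: √(0.80×2/109) = 0.1212, ratio 0.973 (2.7% smaller)

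The ML fits with all covariate-by-time terms agree: 0.1210 to 0.1176 (2.8% smaller) with complete data, and 0.1370 to 0.1328 (3.0%) with missing data. The separate 60-trial set, under other assumed effects, gave ratios 0.941 and 0.951. The range is therefore roughly 1–6%, and zero if the covariates do not predict change.

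The GLS fits with by-time terms for all four covariates gave 0.1224 against 0.1212. There the covariance was held fixed, so a gain could not appear and only the cost of chance covariate imbalance shows.

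**6. Power.** On the plan's own formula, which is not specific to an interaction, 109×0.70/0.75 = 101.7 effective per arm. Then 0.50×√(101.7/2) = 3.57, and power = Φ(3.57−1.96) ≈ 95%. A 1% smaller SE leaves it at about 95%; a 6% smaller SE gives about 97%.

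**The case against.** The strongest reply is that the main effects are not idle in the trial as planned. Section G1 expects 30% attrition, and G2 keeps participants with missing visits in the model. In that setting the terms do move the estimate, and in the simulation they removed a bias of about 0.025 when dropout depended on arm and covariates. This stands: a reader might infer that the covariates do no adjusting at all and could be deleted, and the planned use of incomplete data does not support that.

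Scope also limits the point. The logistic models for dichotomised DDS17, PHQ-8 and GAD-7 are non-linear, and main effects change their coefficients even with complete data (simulated interaction −0.63 without, −0.81 with). The resource-use outcomes test the treatment term itself, so the covariates adjust it directly.

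A reader might also infer that participants who decline to report income are lost. The Missing data paragraph of G2 plans multiple imputation including all variables in the substantive analyses, which largely covers this. The documents give no refusal rate.

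Finally, power is ample at 218 and the gain rests on assumed covariate effects. That is right, and it limits the weight of the point. It does not remove the mismatch between how the trial randomises and what the tested contrast reflects.

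**Conclusion.** The point holds for the linear repeated-measures models of the DDS17 and the continuous secondary outcomes. With complete data the listed main effects leave the time-by-treatment estimate and its SE unchanged; this is exact and rests on no assumption. With 30% attrition the adjustment is weak and the precision gain is 0–2% of the SE in the checks.

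The stratification factor is therefore not carried into the tested contrast. If referral source predicts change, the SE is conservative. The avoidable excess is nil if the covariates do not predict change and roughly 1–6% under assumed modest effects, with the low end corresponding to referral source alone. The documents give no variance components, covariate effects or dropout pattern to narrow this.

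The documents do not support reading this as bias, an inflated false-positive rate or an underpowered trial. Randomisation protects the contrast, and the likely error is on the conservative side.

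**What to change.** In G2, under both the primary outcome and the continuous secondary outcomes, keep the main effects and add referral source-by-time to the linear repeated-measures models. This costs one degree of freedom with linear time or two with categorical time. Because referral source is balanced by stratification, little precision is lost if it turns out not to predict change.

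Optionally add SES-by-time and race/ethnicity-by-time, with few categories fixed in advance. With four levels each for income, education and race/ethnicity (assumed), that is 9 further parameters with linear time or 18 with categorical time, so the case is weaker than for the stratum.

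The text should also say what these terms are for. Two-way covariate-by-time terms describe change common to both arms. They do not test whether SES or race/ethnicity modifies the effect of coaching, which is the reason the plan gives for including them; that would need covariate-by-time-by-treatment terms, labelled exploratory. The change is to analysis wording only and needs no new data or sample size.

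### The stated 80% power at 134 is for the mean of the two follow-up DDS17 scores, not for the time-by-treatment interaction that G2 tests; restate power at 218 for the actual test and use baseline DDS17 efficiently

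*Combined protocol and SAP*

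**What the plan says.** G1 (Sample Size) starts from a two-group t test at one time point (d = 0.50, two-sided 0.05, 80% power). It continues: "this estimate was then adjusted to account for the correlation among the repeated measurements". The factor is [1 + (T-1)rho]/T with T = 2 follow-ups, and rho "is estimated using the relatively high value of 0.5". After inflation for 30% attrition it concludes: "Thus, a sample size of 134 patients would need to be recruited". The recruited number is larger for a different reason, the anxiety and depression outcomes: "we increased the sample size of 134 by 62.7% as described below, resulting in 218 Veterans to be recruited".

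G2 (Data Analysis, primary outcome) describes a random coefficient model: "The random coefficient model will allow us to fit a line for each participant using his/her available data". The model contains "a variable indicating time (baseline, 3 months, or 6 months), and a term for the interaction of time and treatment". The interaction is the term of most interest because "a significant value will indicate a difference between groups over 6 months". On the main effect it says: "The treatment effect will measure differences between the groups at baseline". Referral source, SES and race/ethnicity are a priori covariates.

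Section D states the primary outcome as greater improvement on the DDS17 and names no time point.

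**The concern.** The factor in G1 is the variance of the average of two follow-up scores. Baseline does not enter it. In G2 the group difference at baseline is a free parameter and the tested effect is change from it. These are different contrasts with different variances, so a power figure for one does not carry over to the other.

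The difference also changes what the choice of rho does. For a mean of follow-ups, a higher rho means less independent information and lower power. For change from baseline, a higher rho means that more between-person variation cancels, and power rises. A reader who takes the relatively high 0.5 as a conservative choice would be right about G1's contrast, but not about G2's test.

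G2 also leaves the form of the interaction open. A line per participant suggests numeric time and 1 df. A time variable with three listed values also allows a three-level factor and 2 df. The two forms respond differently to the shape of the effect over time. At stake is whether the protocol states the power of its primary test, and whether that test uses baseline DDS17 as well as it could.

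**Working it through.** **Inputs.** From G1: d = 0.5, two-sided alpha 0.05, 80% power, T = 2, rho = 0.5, 30% loss at 6 months, 134 for the primary outcome, 218 recruited. From F1: 1:1 allocation; visits at baseline, 3 and 6 months. Assumed here: unit variance at each visit; one correlation rho between any two visits, varied over 0.3-0.7; no true baseline difference; d in baseline SDs; monotone loss with 0, 15 or 30 percentage points before month 3 and the rest after. Ranges run over these loss splits.

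**Step 1: reproduce 134.** Normal-approximation t-test size: 62.79 per arm. Times (1 + 0.5)/2 = 0.75: 47.09. Divided by 0.7: 67.3, stated as 67, so 134 in total. Without the 0.75 factor the total is 2 x 62.79/0.7 = 179. The figure therefore depends on the variance of a mean of two follow-ups, (1 + rho)/2.

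**Step 2: completers by hand.** Over three equally spaced visits the straight-line contrast weights the visits -1, 0, +1. It is the 6-month minus baseline change, with variance 2(1 - rho). At 134 there are 67 x 0.7 = 46.9 completers per arm. With rho = 0.5:

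- Follow-up mean, variance 0.75: 0.5/sqrt(2 x 0.75/46.9) = 2.80; power = Phi(2.80 - 1.96), about 80%.
- Slope, variance 1.00: 0.5/sqrt(2 x 1.00/46.9) = 2.42; power = Phi(2.42 - 1.96), about 68%.

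The two variances are equal when (1 + rho)/2 = 2(1 - rho), that is at rho = 0.6. Below that the slope is the weaker test; above it, the stronger.

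**Step 3: all available data.** G2 keeps participants with missing visits, so completer figures understate its power. Generalised least squares was used: the information matrix sums (N/2) w X'V^-1 X over arms and loss patterns (w = share of the arm with that pattern), and the interaction is tested by a noncentral F with 1 or 2 numerator df and N - 2 denominator df. The G1 row uses a noncentral t on 0.7N completers.

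Power (%) at 134, effect 0.5 at both follow-ups:

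| Test | rho 0.3 | rho 0.5 | rho 0.7 |
|---|---|---|---|
| G1: mean of follow-ups, completers | 84 | 79 | 74 |
| G2 as a straight line, 1 df | 61-65 | 73-79 | 90-95 |
| G2 as a three-level factor, 2 df | 61-67 | 74-82 | 92-97 |

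The first row falls with rho; the other two rise.

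**Step 4: the recruited 218, rho 0.5.** The patterns are illustrative.

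| Effect at month 3 / month 6 | Slope, 1 df | 2 df | Slope, common baseline |
|---|---|---|---|
| 0.50 / 0.50 | 91-94 | 93-96 | 98-99 |
| 0.50 / 0.25 | 41-54 | 82-92 | 63-83 |
| 0 / 0.50 | 85-88 | 91 | 88-91 |

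At rho 0.3 with a sustained effect, the slope at 218 has 81-85% and the 2-df test at least 83%.

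**The case against.** The strongest reply is that nothing is short. The trial recruits 218, not 134, and at G1's own rho either form of the interaction exceeds 90% for a sustained effect. Even at rho 0.3 the slope needs 189-211 recruited for 80%, still below 218. G1 also cites 16.9% attrition in a related study, so 30% loss may be pessimistic. All of this stands. A reader might infer from the mismatch that the primary outcome is underpowered; on the plan's inputs it is not.

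Second, a reader might infer that 0.5 errs on the unsafe side. That holds only if the true correlation is lower. The documents give no other DDS17 correlation, and above 0.5 the interaction does better than shown. What stands is that the cautious direction differs between the two tests.

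Third, a reader might infer from the end of the intervention at month 3 that the effect will wane and G2 will miss it. The documents predict no trajectory, and F2 gives a reason for persistence, since coaches link Veterans to continuing programs. The weakness under waning belongs to the straight-line coding alone, and part of it is simply the smaller month-6 effect.

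Fourth, the average of months 3 and 6 is not the obvious replacement. With a common baseline, at 218 and rho 0.5, it has 90-95% if the effect halves by month 6, but only 58-68% if the effect appears only at month 6.

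**Conclusion.** The point holds as a mismatch between the sample-size justification and the primary test. The 80% at 134 belongs to an unadjusted mean of two follow-ups. For the interaction in G2 the same 134 gives 73-79% (slope) or 74-82% (2 df) at rho 0.5, and 61-67% across both codings at rho 0.3. The 2-df reading is thus consistent with 80% at rho 0.5, but only there. G1 gives no power at 218 for the test to be run, although the answer is reassuring for a sustained effect.

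The coding of time matters to the result only if the effect is not sustained: at 218 and rho 0.5, halving by month 6 gives 41-54% under one permitted reading and 82-92% under the other.

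Leaving the baseline difference free also gives up precision: equal baseline means, which randomization justifies, would lift the sustained slope from 91-94% to 98-99%.

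These figures rest on equal correlations between visits, d = 0.5 and 30% loss. The mismatch itself follows from the text and needs none of them.

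**What to change.** Before outcome data are seen:

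1. In G1, replace 80% at 134 as the primary-outcome power with power at 218 for the interaction or contrast actually tested, shown over rho 0.3 to 0.7. State that low rho is the unfavourable case for a change from baseline, and high rho for an unadjusted mean of follow-ups.
2. In G2, constrain mean baseline DDS17 to be equal in the two arms, or pre-specify baseline DDS17 as a covariate, keeping the referral-source, SES and race/ethnicity terms. Because this is pre-specified, it does not conflict with G2's refusal to adjust for variables found to differ. It relies on baseline DDS17 being collected before the participant learns the allocation. F2 places both randomization and the baseline assessment after consent without giving their order. It keeps allocation from the baseline evaluator but is silent on the participant. Confirm the order there.
3. In the same edit, name the one primary contrast with its time coding and degrees of freedom. The average of months 3 and 6, the 2-df interaction, the slope and the baseline-adjusted month-6 difference are all legitimate; the choice is the sponsor's.

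The cost is wording and a short power recalculation, with no new patients, visits or data. The restated power will look less favourable at the low end of rho.
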